221 Administration of herbal supplements, vitamins, or nutritional supplements within 30 days prior to the first dose of investigational product, and continuing use, if applicable, will be reviewed by the Investigator and the Amgen Medical Monitor to determine acceptability. Written documentation of this review and Amgen acknowledgment is required for subject participation.

Prior/Concurrent Clinical Study Experience

222 Currently receiving treatment in another investigational device or drug study, or less than 30 days at day 1 since ending treatment on another investigational device or drug study(ies). Other investigational procedures while participating in this study are excluded.

223 Subject previously enrolled in this study may not be re-enrolled *unless* they fulfill the following criteria:

- Have completed the study previously without any adverse events deemed related to study drug.
- Have received the last dose of AMG 592/placebo > 6 months prior to the screening visit.
- Must not have tested positive for neutralizing antibodies against AMG 592 at any time.

Diagnostic Assessments

224 Presence of laboratory abnormalities at screening including the following:

- Aspartate aminotransferase (AST) or alanine aminotransferase (ALT) > 1.5 x upper limit of normal (ULN).
- Serum total bilirubin (TBL) \geq 1.5 mg/dL (\geq 26 μ mol/L)
- Hemoglobin < 9.0 g/dL (< 90 g/L)
- Platelet count < 100,000/mm³ (100 x 10⁹/L)
- White blood cell count < 2,000 cells/mm³ (2.0 x 10⁹/L)
- Absolute neutrophil count (ANC) < 1,000/mm³ (1.0 x 10⁹/L)
- Calculated glomerular filtration rate of \leq 50 mL/min/1.73 m² using the Modification of Diet in Renal Disease (MDRD) formula.

225 Any other laboratory abnormality, which, in the opinion of the investigator, poses a safety risk, will prevent the subject from completing the study, will interfere with the interpretation of the study results, or might cause the study to be detrimental to the subject.

Other Exclusions

226 Female subject is pregnant or breastfeeding or planning to become pregnant or breastfeed during treatment and for an additional 6 weeks after the last dose of investigational product.

227 Females of child-bearing potential with a positive pregnancy test (assessed by a serum pregnancy test at screening and a urine pregnancy test at baseline).

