- Wilson's disease and hemochromatosis
- Nonalcoholic fatty liver disease including steatohepatitis
- Non-hepatic causes (eg, rhabdomylosis, hemolysis)

If investigational product(s) is/are withheld, the subject is to be followed for possible drug-induced liver injury (DILI) according to recommendations in the last section of this appendix.

Approved

Rechallenge may be considered if an alternative cause for impaired liver tests (ALT, AST, ALP) and/or elevated TBL, is discovered and the laboratory abnormalities resolve to normal or baseline (see next section in this appendix).

Table 12-2. Conditions for Withholding and/or Permanent Discontinuation of Amgen Investigational Product and Other Protocol-required Therapies due to Potential Hepatotoxicity

Analyte	Temporary Withholding	Permanent Discontinuation
TBL	> 3 x ULN at any time	> 2 x ULN OR
INR	--	> 1.5 x ULN (for subjects not on anticoagulation therapy) OR AND
AST/ALT	> 8 x ULN at any time > 5 x ULN but < 8 x ULN for \geq 2 weeks > 5 x ULN but < 8 x ULN and unable to adhere to enhanced monitoring schedule > 3 x ULN with clinical signs or symptoms that are consistent with hepatitis (such as right upper quadrant pain/tenderness, fever, nausea, vomiting, and jaundice)	In the presence of no important alternative causes for elevated AST/ALT and/or TBL values > 3 x ULN (when baseline was < ULN)
ALP	> 8 x ULN at any time	--

ALP = alkaline phosphatase; ALT = alanine aminotransferase; AST = aspartate aminotransferase; INR = international normalized ratio; TBL = total bilirubin; ULN = upper limit of normal

Criteria for Rechallenge of Amgen Investigational Product and Other Protocol-required Therapies After Potential Hepatotoxicity

The decision to rechallenge the subject is to be discussed and agreed upon unanimously by the subject, investigator, and Amgen.

If signs or symptoms recur with rechallenge, then investigational product is to be permanently discontinued. Subjects who clearly meet the criteria for permanent discontinuation (as described in [Table 12-2](#)) are never to be rechallenged.

Drug-induced Liver Injury Reporting and Additional Assessments

Reporting

To facilitate appropriate monitoring for signals of DILI, cases of concurrent AST or ALT and TBL and/or INR elevation, according to the criteria specified in the above, require the following:

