- The event is to be reported to Amgen as a serious adverse event within 24 hours of discovery or notification of the event (ie, before additional etiologic investigations have been concluded)
- The appropriate case report form (CRF) (eg, Event CRF) that captures information necessary to facilitate the evaluation of treatment-emergent liver abnormalities is to be completed and sent to Amgen

Other events of hepatotoxicity and potential DILI are to be reported as serious adverse events if they meet the criteria for a serious adverse event defined in [Appendix 4](#).

Additional Clinical Assessments and Observation

All subjects in whom investigational product(s) or protocol-required therapies is/are withheld (either permanently or conditionally) due to potential DILI as specified in [Table 12-2](#) or who experience AST or ALT elevations $> 3 \times$ upper limit of normal (ULN) or 2-fold increases above baseline values for subjects with elevated values before drug are to undergo a period of “close observation” until abnormalities return to normal or to the subject’s baseline levels.

Assessments that are to be performed during this period include:

- Repeat AST, ALT, ALP, BIL (total and direct), and INR within 24 hours
- In cases of TBL $> 2 \times$ ULN or INR > 1.5 , retesting of liver tests, BIL (total and direct), and INR is to be performed every 24 hours until laboratory abnormalities improve

Testing frequency of the above laboratory tests may decrease if the abnormalities stabilize or the investigational product(s) or protocol-required therapies has/have been discontinued AND the subject is asymptomatic.

Initiate investigation of alternative causes for elevated AST or ALT and/or elevated TBL.

The following are to be considered depending on the clinical situation:

- Complete blood count with differential to assess for eosinophilia
- Serum total immunoglobulin G, antinuclear antibody, anti smooth muscle antibody, and liver kidney microsomal antibody-1 to assess for autoimmune hepatitis
- Serum acetaminophen (paracetamol) levels

Approved

- A more detailed history of:
 - Prior and/or concurrent diseases or illness
 - Exposure to environmental and/or industrial chemical agents
 - Symptoms (if applicable) including right upper quadrant pain, hypersensitivity-type reactions, fatigue, nausea, vomiting and fever
 - Prior and/or concurrent use of alcohol, recreational drugs and special diets

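### Eligible subjects with baseline AST/ALT at or above ULN have no permanent-discontinuation condition in Table 12-2 for combined AST/ALT and TBL/INR elevation

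*Protocol*

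**What the plan says.** - **Entry.** Protocol Section 6.2, criterion 224, lists among the excluded screening abnormalities "Aspartate aminotransferase (AST) or alanine aminotransferase (ALT) > 1.5 x upper limit of normal (ULN"). Values from ULN up to and including 1.5 x ULN are therefore allowed.
- **Permanent discontinuation.** In Appendix 7, Table 12-2, this column has a TBL condition (above 2 x ULN), an INR condition ("> 1.5 x ULN (for subjects not on anticoagulation therapy) OR AND") and an AST/ALT condition ("> 3 x ULN (when baseline was < ULN")), in the absence of an important alternative cause.
- **Temporary withholding.** The same table has separate conditions with no reference to baseline: TBL above 3 x ULN, ALP above 8 x ULN, several AST/ALT conditions above 5 x ULN, and AST/ALT "> 3 x ULN with clinical signs or symptoms that are consistent with hepatitis".
- **Rechallenge.** Appendix 7 bars rechallenge for one group: "Subjects who clearly meet the criteria for permanent discontinuation (as described in" Table 12-2). Separately, "If signs or symptoms recur with rechallenge, then investigational product is to be permanently discontinued".
- **Reporting.** Appendix 7 requires a 24-hour SAE report for "cases of concurrent AST or ALT and TBL and/or INR elevation, according to the criteria specified in the above".
- **Close observation.** The last part of Appendix 7 applies to any AST or ALT above 3 x ULN and also to "2-fold increases above baseline values for subjects with elevated values before drug".

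**The concern.** The entry criterion and one cell of the liver stopping rule use different limits. Criterion 224 admits subjects whose transaminases are already raised, and the close-observation paragraph expects them. The permanent-discontinuation cell does not provide for them.

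The rule for combined transaminase and bilirubin or INR elevation is meant to give all sites the same instruction. For eligible subjects with a baseline at or above ULN, the table gives none. Two further provisions depend on that cell. The ban on rechallenge applies to those who meet the permanent criteria, so it cannot reach these subjects through the table. The automatic SAE report refers back to the stated criteria, so a site cannot tell whether it applies to them. Safety is the primary objective, and approximately 20 sites are planned (Section 5.2.2), so an ambiguous instruction could be handled differently from site to site.

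**Working it through.** The plan states no figure to reproduce. The check sets the conditions out as logical rules and applies them to the same on-study values at different baselines. All values are multiples of ULN.

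**Inputs**

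- Eligible (criterion 224): screening AST and ALT not above 1.5.
- Permanent (Table 12-2): (TBL > 2 or INR > 1.5) and AST/ALT > 3 and baseline < 1 and no important alternative cause.
- Temporary (Table 12-2): TBL > 3; or ALP > 8; or AST/ALT > 8; or AST/ALT between 5 and 8 for at least 2 weeks or without adherence to enhanced monitoring; or AST/ALT > 3 with hepatitis signs or symptoms.

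**How the permanent column is joined.** The extracted table runs the connectors together, so the AND needs support from elsewhere. The reporting sentence speaks of concurrent elevation. The thresholds point the same way: if TBL above 2 alone meant permanent discontinuation, the temporary condition at TBL above 3 would never be the operative one. The combined reading is the one that makes the table coherent.

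**Results** (asymptomatic, no alternative cause, not on anticoagulation, ALP not above 8)

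| Baseline ALT | On-study ALT | TBL | INR | Permanent | Temporary |
|---|---|---|---|---|---|
| 0.9 | 4 | 2.5 | 1.0 | met | not met |
| 1.2 | 4 | 2.5 | 1.0 | not met | not met |
| 0.9 | 4 | 1.0 | 1.8 | met | not met |
| 1.2 | 4 | 1.0 | 1.8 | not met | not met |
| 0.9 | 9 | 2.5 | 1.0 | met | met |
| 1.2 | 9 | 2.5 | 1.0 | not met | met |
| 0.9 | 4 | 3.5 | 1.0 | met | met |
| 1.2 | 4 | 3.5 | 1.0 | not met | met |

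A baseline of 0.99 behaves as 0.9. Baselines of 1.0 and 1.5 behave as 1.2. A screening value of 1.51 is excluded.

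**Reading the table**

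- Rows 1 and 2: TBL 2.5 is not above 3, ALT 4 is not above 5, and there are no symptoms. At baseline 1.2 neither column is met, while the same values at baseline 0.9 require permanent discontinuation. Rows 3 and 4 show the same through INR.
- Rows 5 to 8: at more extreme values the subject with the raised baseline reaches temporary withholding but never the permanent condition.
- With ALT at 4, close observation applies in every row with that value, whatever the baseline. Where TBL is above 2 or INR above 1.5, it includes retesting every 24 hours until improvement.

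So for a baseline at or above ULN, neither column is met when the subject is asymptomatic, AST/ALT is above 3 and up to 5 (or between 5 and 8 for less than 2 weeks with monitoring kept up), and either TBL is above 2 and up to 3, or INR is above 1.5 with TBL not above 3.

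**Which baselines are affected.** Criterion 224 applies at screening. Chemistry is repeated on Day -1 (Table 2-1), and SAP Section 5.2 takes baseline as the last assessment up to first dosing. A subject can therefore move into or out of the affected range after screening, so it is only approximately ULN to 1.5 x ULN.

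**The case against.** A reader might infer that these subjects have no liver stopping rule, or that a combined elevation in them would be lost to the primary safety data and to the Dose Level Review Meeting (DLRM). The documents do not support either inference.

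- All temporary-withholding conditions apply at any baseline, including AST/ALT above 3 x ULN with symptoms such as jaundice, nausea or fever. The uncovered region needs a subject with none of these.
- Close observation requires repeat liver tests and INR within 24 hours and a search for other causes. If TBL passes 3 x ULN or AST/ALT passes 8 x ULN, withholding follows.
- Sections 8 and 8.1 let the investigator or sponsor withdraw a subject from product for an adverse event or by sponsor decision. The table's silence does not compel continued dosing.
- Appendix 7 contemplates rechallenge only if an alternative cause is found and the abnormalities resolve, and only by unanimous agreement. If signs or symptoms recur, product stops for good at any baseline.
- Other potential drug-induced liver injury is reported as an SAE if it meets Appendix 4, which includes medically important events. Appendix 7 requires CRF capture, the DLRM reviews laboratory results (Appendix 3), and SAP Section 9.6.3 tabulates shifts to the worst CTCAE grade.

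A reader might also compute that one such subject is 1/5 = 20% or 1/3 = 33% of a cohort's active data. That assumes the subject exists and says nothing about how likely the combined elevation is. Section 3.3 reports no clinically significant treatment-related biochemical abnormalities to date. Finally, Appendix 7 cites an outside guidance that is not available here, and its title calls the actions suggested.

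All of this stands as a limit on the consequences. None of it supplies the missing condition: observation does not direct the site to stop, withdrawal under Section 8.1 is discretionary, and withholding starts at other thresholds.

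**Conclusion.** The gap is real and narrow. Criterion 224 admits subjects with screening AST/ALT from ULN to 1.5 x ULN, and Table 12-2 gives those whose baseline is at or above ULN no permanent-discontinuation condition for combined AST/ALT and TBL/INR elevation. Identical on-study values lead to different instructions, and the subject with pre-existing elevation receives the weaker one. Through the table, the ban on rechallenge does not reach this subject, and the automatic 24-hour SAE report is ambiguous.

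The size is one cell of the stopping rule, with no loss of safety data. The number of subjects affected cannot be estimated, because the documents give no frequency of raised baseline values or of combined elevations. The conclusion rests on reading the permanent column as a combined condition, and on the table as extracted containing no further baseline clause; nothing in the text suggests one.

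**What to change.** Reconcile criterion 224, Table 12-2 and the close-observation paragraph of Appendix 7 so that every baseline AST/ALT value an eligible subject can have, including ULN and above, falls under a stated permanent-discontinuation condition. State which measurement counts as baseline for the table, since screening and Day -1 values can differ. Tie the SAE reporting sentence to the reconciled table; the ban on rechallenge already refers to it and will follow. The sponsor sets the condition, and no threshold is proposed here.

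The cost is a row or clause in Table 12-2 and a small edit to the reporting sentence, by amendment, with no extra tests. The downside is that a few more subjects could meet a discontinuation condition.

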**List of Abbreviations**

Abbreviation or Term	Definition/Explanation
Anti-dsDNA	Anti-double stranded DNA
AUC	area under the concentration-time curve
AUC tau	area under the concentration-time curve over a dosing interval
BLRM	Bayesian logistic regression model
C max	maximum observed concentration
CPMS	Clinical Pharmacology Modeling and Simulation
CRF	case report form
CTCAE	common terminology criteria for adverse events
DLRM	dose level review meeting
ECG	Electrocardiogram
End of Follow-up	defined as when the last subject completes the last protocol-specified assessment in the study
End of Study for Individual Subject	defined as the last day that protocol-specified procedures are conducted for an individual subject
End of Study (primary completion)	defined as the date when the last subject is assessed or receives an intervention for the final collection of data for the primary endpoint(s), for the purposes of conducting the primary analysis, whether the study concluded as planned in the protocol or was terminated early
End of Study (end of trial)	defined as the date when the last subject is assessed or receives an intervention for evaluation in the study (ie, last subject last visit), following any additional parts in the study (eg, long-term follow-up), as applicable
GSO-DM	The Amgen Global Study Operations-Data Management
IL-2	Interleukin 2
IP	Investigational Product
IPD	Important Protocol Deviations
IRT	interactive response technology that is linked to a central computer in real time as an interface to collect and process information
ISR	Injection Site Reaction
MAD	multiple ascending dose
MedDRA	Medical Dictionary for Regulatory Activities
NK cells	natural killer cells
PD	Pharmacodynamic
PK	Pharmacokinetic

PR Interval	PR interval is measured from the beginning of the P wave to the beginning of the QRS complex in the heart's electrical cycle as measured by ECG
QRS interval	QRS interval is the interval between the Q wave and the S wave in the heart's electrical cycle as measured by ECG; represents the time it takes for the depolarization of the ventricles
QT interval	QT interval is a measure of the time between the start of the Q wave and the end of the T wave in the heart's electrical cycle as measured by ECG.
QTc interval	QT interval corrected for heart rate using accepted methodology
QW	every week
Q2W	every other week
SAE	Serious Adverse Events
SAP	Statistical Analysis Plan
SC	Subcutaneous
SLE	systemic lupus erythematosus
SLEDAI-2K	Systemic Lupus Erythematosus Disease Activity Index 2000
Source Data	Information from an original record or certified copy of the original record containing patient information for use in clinical research. The information may include, but is not limited to, clinical findings, observations, or other activities in a clinical trial necessary for the reconstruction and evaluation of the trial. Source data are contained in source documents (original records or certified copies). (ICH Guideline [E6]). Examples of source data include Subject identification, Randomization identification, and Stratification Value.
Tcon	conventional T cell
T max	time of maximum observed concentration
TEAE	Treatment Emergent Adverse Events
Treg	regulatory T cells

---

**1. Introduction**

The purpose of this Statistical Analysis Plan (SAP) is to provide details of the statistical analyses that have been outlined within the superseding protocol amendment 5 for study 20170103, AMG 592 dated 25 June 2020. The scope of this plan includes the analysis for dose level review meetings (DLRM) and the final analysis that is planned and will be executed by the Amgen Global Biostatistical Science department unless otherwise specified.

**2. Objectives, Endpoints and Hypotheses**

**2.1 Objectives and Endpoints/Estimands**

Objectives	Endpoints
Primary	

To evaluate the safety and tolerability of subcutaneous (SC) dose administrations of AMG 592 in subjects with systemic lupus erythematosus (SLE)

	

Treatment-emergent adverse events

Clinically significant changes in physical examinations, vital signs, and laboratory safety tests

Secondary	

To characterize the pharmacokinetic (PK) profile following treatment with AMG 592

	

AMG 592 serum concentration and PK parameters including, but not limited to, maximum observed concentration (Cmax), the time of maximum observed concentration (Tmax), and area under the concentration-time curve over a dosing interval (AUCtau) after the first and last doses

To evaluate anti-AMG 592 antibody formation

	

Incidence of anti-AMG 592 antibodies

Cross-reactivity of anti-AMG 592 antibodies with human interleukin-2 (IL-2)

Incidence of anti-AMG 592 and anti-IL 2 neutralizing antibodies

Exploratory	

To explore the effect of treatment with AMG 592 on measures of inflammation at various time points

	

Change from baseline in anti-double stranded DNA (anti-dsDNA), and C3 and C4 complements at all time points collected

To explore the effect of treatment with AMG 592 on measures of disease activity at various time points

	

SLEDAI-2K score and change from baseline at all time points collected

To evaluate the immunological effects of AMG 592

	

Fold changes from baseline of Treg, Tcon, and NK absolute cell counts (cells/<math>\mu</math>L) after AMG 592 administration

Changes in Treg/Tcon ratio after AMG 592 administration

## 2.2 Hypotheses and/or Estimations

AMG 592 will be safe and well tolerated in subjects with SLE. There is no formal hypothesis planned for the study.

### 3. Study Overview

#### 3.1 Study Design

This phase 1b study is a double-blind, placebo-controlled, multiple ascending dose (MAD) study to evaluate the safety, tolerability, PK, immunogenicity, and PD of AMG 592 in subjects with SLE. Subjects will be treated for a total of 12 weeks after which they will be followed for an additional 6 weeks for safety and additional PK/PD data collection.

Five dosing cohorts are planned for the study. For cohorts 1, 2, and 3, subjects within a dosing-cohort will be randomized in a 5:2 ratio to AMG 592 (n = 5) or placebo (n = 2) as follows: cohort 1 (████ μg ████████); cohort 2 (████ μg █████); and cohort 3 (████ μg ████████), in addition to standard of care therapy. For cohorts 4 and 5, subjects within a dosing-cohort will be randomized in a 3:1 ratio to AMG 592 (n = 3) or placebo (n = 1) as follows: cohort 4 (████ μg █████) and cohort 5 (████ μg █████), in addition to standard of care therapy. Dosing cohorts will enroll sequentially. A Dose Level Review Meeting (DLRM) will convene after the last subject in each cohort completes the week 4 visit. The decision to dose the next cohort will be based on the aggregated review of safety data. After incidents of interest (including selected adverse events or intolerable PD levels) are observed, a Bayesian logistic regression model (BLRM) if required will be implemented to model these events before each DLRM to aid dosing recommendations. Dose Level Review Meeting members will be responsible for dosing recommendations, which may include escalation to the next planned dose or a new higher dose, escalation to an intermediate dose (a dose lower than the next planned dose), de-escalation to a lower dose; continuation, delay, or termination of dosing. Additional dosing cohorts may be added and/or existing cohorts may be expanded based on emerging data. Dose Level Review Meeting members may also consider available aggregated summaries of emerging PK and PD data. Amgen DLRM members may consider safety, PK and PD data from other completed and ongoing phase 1b studies to aid dosing recommendations. Emerging safety, PK, and PD data from ongoing AMG 592 studies may be used to support recommendations to skip dosing cohorts, reduce dosing cohort size or change doses for a given cohort or stop the study entirely.

